9.2.2 Supplementary Analysis of the Primary Efficacy Endpoint

[figure not shown]
For the primary efficacy endpoint, the same CMH analysis as detailed in Section 9.2.1 will be repeated using As Observed (AO) data handling without any imputation as supplementary analysis. This will be conducted on the FAS based on randomized treatment groups. The corresponding estimand for the supplementary analysis is the difference in the proportion of PsA patients who achieved ACR20 response at Week 12, regardless of whether the subject had discontinued study drug by Week 12, comparing each upadacitinib dose group vs placebo. The analysis will be conducted for those who are randomized, received study drug and have the efficacy measurement at Week 12 visit.

In addition to the supplementary analysis based on AO data, to explore various missing data assumptions including missing not at random (MNAR), tipping point analysis will also be performed for the primary endpoint by multiple imputations using logistic regression, allowing the imputed ACR response rate to systematically vary from 0% to 100% in both upadacitinib and placebo, respectively. Details of the tipping point analysis are outlined in Appendix B. Supportive analysis will also be conducted on the Per Protocol Analysis Set using the CMH model and NRI data handling.

9.2.3 Key Secondary Efficacy Analyses

The following is a list of ranked key secondary endpoints (upadacitinib versus placebo if not otherwise specified):

[figure not shown]
- 1. Change from baseline in HAQ-DI at Week 12;
- Static Investigator Global Assessment (sIGA) of Psoriasis of 0 or 1 and at least a 2-point improvement from baseline at Week 16 (for subjects with baseline sIGA ≥ 2);

- 3. Psoriasis Area Severity Index (PASI) 75 response at Week 16 (for subjects with ≥ 3% BSA psoriasis at baseline);
- 4. Change from baseline in modified PsA Sharp/van der Heijde Score (SHS) at Week 24;
- 5. Proportion of subjects achieving MDA at Week 24;
- 6. Proportion of subjects with resolution of enthesitis (LEI = 0) at Week 24 (for subjects with baseline presence of enthesitis (LEI > 0));
- 7. ACR 20 response rate at Week 12 (non-inferiority of upadacitinib vs adalimumab);
- 8. Change from baseline in SF-36 PCS at Week 12;
- 9. Change from baseline in FACIT-Fatigue at Week 12;
- 10. ACR 20 response rate at Week 12 (superiority of upadacitinib vs. adalimumab);
- 11. Proportion of subjects with resolution of dactylitis (LDI = 0) at Week 24 (for subjects with baseline presence of dactylitis (LDI > 0));
- 12. Change from baseline in Patient's Assessment of Pain NRS at Week 12 (superiority of upadacitinib vs. adalimumab);
- 13. Change from baseline in HAQ-DI at Week 12 (superiority of upadacitinib vs. adalimumab);
- 14. Change from baseline in Self-Assessment of Psoriasis Symptoms (SAPS) at Week 16.

Additional key secondary efficacy endpoints are:

- 1. ACR50/70 response at Week 12;
- 2. ACR20 response at Week 2.

[figure not shown]
Binary Endpoints

For binary endpoints, frequencies and percentages will be reported for each treatment group. For the ranked secondary endpoints at the time point of interest, the primary estimand is the same as that for the primary efficacy endpoint as defined in Section 9.2.1, except for the definition of the efficacy measurement.

For the key secondary endpoints applicable only for sub-population, the estimands will be constructed similarly but based on the sub-population, as defined in the below table.

Endpoint	Sub-population
Static Investigator Global Assessment (sIGA) of Psoriasis of 0 or 1 and at least a 2 point improvement from baseline at Week 16	Subjects with baseline sIGA ≥ 2 are included in the analysis
Psoriasis Area Severity Index (PASI) 75 response at Week 16	Subjects with \geq 3% BSA psoriasis at baseline are included in the analysis
Proportion of subjects with resolution of enthesitis (LEI = 0) at Week 24	Subjects with baseline LEI > 0 are included in the analysis
Proportion of subjects with resolution of dactylitis at Week 24	Subjects with baseline LDI > 0 are included in the analysis

For MDA at Week 24, resolution of enthesitis at Week 24 and resolution of dactylitis at Week 24, in addition to the NRI data handling as defined in Section 9.1.2, subjects who meet the rescue criteria (i.e., not achieving at least 20% improvement in either or both tender joint count (TJC) and swollen joint count (SJC) at both Week 12 and Week 16) will also be treated as non-responders. The corresponding primary estimand is the difference in the proportion of patients who achieved MDA/resolution of enthesitis/resolution of dactylitis at Week 24, and who did not discontinue study drug and did not initiate rescue therapy by Week 24. The comparison is for each upadacitinib dose group vs placebo for patients randomized and treated with at least one dose of study drug. NRI data handling will be used to analyze the primary estimand for binary endpoints.

Supplementary analysis using AO data handling will also be conducted. The corresponding supplementary estimand is the same as defined in Section 9.2.2 except for the definition of the efficacy measurement.

[figure not shown]
Point estimate and 95% CI using normal approximation will be provided for the response rate for each randomized treatment group. Treatment comparisons will be made between each upadacitinib dose and the combined placebo group using the Cochran-Mantel-Haenszel test (refer to Appendix A). The CMH test adjusts for the main stratification factor of current DMARD use (yes/no). Point estimate, 95% CI using normal approximation and the p-value for the treatment difference will be presented.

For ACR20 response at Week 12, analysis will be conducted to assess the non-inferiority of each upadacitinib dose versus adalimumab on the placebo-subtracted treatment difference using Koch's 3-arm test statistic as described in Appendix C. The test aims to show that upadacitinib preserves at least 50% of the placebo-subtracted adalimumab effect. If statistical significance is achieved for the non-inferiority assessment, superiority of upadacitinib versus adalimumab will be tested for ACR20 subsequently as described in Section 9.2.5.

Non-Radiographic Continuous Endpoints

For non-radiographic continuous endpoints, the estimand is the difference in mean change from baseline at the protocol defined time point (e.g., HAQ-DI at Week 12) under the assumption that patients with missing data, including those due to premature discontinuation of study drug, can have their measurements at the protocol defined time point predicted by their observed data and the observed data for other patients for their respective assessments during follow-up. The comparison is for each upadacitinib dose group vs placebo for patients randomized and treated with at least one dose of study drug.

To analyze the primary estimand for the continuous ranked secondary efficacy endpoints, statistical inference will be conducted using the MMRM model and the associated data handling as described in Section 9.1.2, with fixed effects of treatment, visit, treatment-by-

[figure not shown]
visit interaction, the stratification factor of current DMARD use (yes/no) and the continuous fixed covariate of baseline measurement. The LS mean and 95% CI for each randomized treatment group and the LS mean treatment difference, the associated 95% CI and the p-value between each upadacitinib dose group and the combined placebo group will be provided. For change from baseline in Patient's Assessment of Pain NRS and change from baseline in HAQ-DI at Week 12, superiority of upadacitinib vs. adalimumab will also be tested using the same MMRM model.

The supplementary analysis for ranked non-radiographic secondary continuous endpoints will be conducted using AO data handling and using the analysis of covariance (ANCOVA) model with treatment and the stratification factor of current DMARD use (yes/no) as the fixed factors and the corresponding baseline values as the covariates. The corresponding estimand is the difference in the mean change from baseline in the efficacy endpoints at the protocol defined time point regardless of treatment discontinuation or use of rescue medication, comparing each upadacitinib dose group vs placebo. The analysis will be conducted for those who are randomized, received study drug and have the efficacy measurement at the protocol defined time point.

For the key continuous endpoint change from baseline in HAQ-DI at Week 12, tipping point analysis will also be conducted using multiple imputation (MI) as additional supplementary analysis to explore various missing data assumptions including missing not at random (MNAR). Details of the tipping point analysis for continuous endpoints are outlined in Appendix D.

Radiographic Endpoints

For change from baseline in SHS at Week 24, statistical inference will be conducted using ANCOVA model and the associated data handling as described in Section 9.1.2 with treatment and the stratification factor of current DMARD use (yes/no) as the fixed factors and the corresponding baseline values as the covariates. The primary estimand for the x-ray assessment is the difference in the mean change from baseline in SHS score at Week 24, under the assumption that patients with missing data, including those due to

premature discontinuation of study drug or use of rescue medication, can have their measurements at Week 24 predicted using their SHS score from the baseline window and the Week 16 window. The comparison will be between each upadacitinib dose group vs placebo for patients randomized and treated with at least one dose of study drug.

To incorporate the uncertainty of a single imputation, the Multiple Imputation (MI) analysis will be conducted as a sensitivity analysis. The proposed MI model for the change from baseline in SHS score will be based on the linearity assumption for the subjects with missing data including those due to premature discontinuation of study drug or meeting the rescue criteria. More specifically, the regression method will be used where missing Week 24 observations will be imputed by regression upon all previous visits including baseline and Week 16, stratified by treatment group. The imputation model will also include baseline demographics and key baseline characteristics as appropriate. Analysis of covariance (ANCOVA) will be performed on each of the multiple imputed datasets. The results will be aggregated across the multiple imputed datasets using Rubin's method. The detailed SAS procedure are outlined in Appendix D.

The supplementary analysis will be performed using AO data handling with the same ANCOVA model. The corresponding estimand for the AO analysis is the difference in the mean change from baseline in SHS score at Week 24, regardless of premature discontinuation of study drug or use of rescue medication, comparing each upadacitinib dose group vs placebo. The analysis will be conducted for those who are randomized, received study drug and have the efficacy measurement at Week 24 visit.

The LS mean and 95% CI for each randomized treatment group and the LS mean treatment difference, the associated 95% CI and the p-value between each upadacitinib dose group and the combined placebo group will be provided.

In another sensitivity analysis, a random coefficient model will be applied, in which SHS measurements are used as the response variable, including measurements at Baseline and post-Baseline. The model is specified with a random intercept and a random slope on time, and includes treatment, current DMARD use (yes/no), and treatment-by-time

interaction in the model. The "group" option in PROC MIXED is used to allow for heterogeneity among treatment groups in the covariance structure. The coefficient for treatment-by-time interaction is used to estimate the difference in rate of progression (per 24 weeks) comparing upadacitinib and placebo. The rate of progression (per 24 weeks) for each group respectively is also estimated using the coefficients for time and treatment-by-time interaction. In case the random coefficient model does not converge, a simplified model may be explored by removing the random intercept or fitting a fixed-effect linear effect model.

Additionally, in the event that data severely deviates from the normal distribution, non-parametric analyses such as the ranked ANCOVA may be considered for treatment comparison.

[figure not shown]

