- m. X-rays of hands and feet will be performed for all subjects at Screening, Wk 24, Wk 56, Wk 104, Wk 152 and Wk 260/PD visits. All subjects who fail to attain at least 20% improvement in either or both TJC and SJC at Week 12 and Week 16 will have an x-ray examination at Week 16. An x-ray examination at Week 16 is not required for subjects with at least a 20% improvement in either or both TJC and SJC at Week 12 and Week 16. All subjects will receive x-rays of hands and feet if they discontinue from the study or from study drug at Week 12 or later and it has been at least 12 weeks from when x-rays were last obtained during Period 1 or at least 24 weeks during Period 2.
- n. Randomization is permitted prior to results of the central reading of hand and foot x-rays for eligibility if a subject has an elevated hs-CRP available from the central laboratory and all other criteria are met.
- o. For all women of childbearing potential, collect serum for pregnancy test at Screening and if any urine pregnancy test is positive at any time during the study. If the serum pregnancy test is positive the subject is considered a screen failure. If serum pregnancy test comes back borderline, a repeat test is necessary (pregnancy is an exclusion criterion). If still borderline ≥ 3 days later, this will be considered documentation of continued lack of a positive result and the subject can be enrolled into the study. Refer to Section 5.3.1.1 Study Procedures Pregnancy Test for additional details.

[figure not shown]
- p. For all female subjects of childbearing potential, collect urine for pregnancy test at Baseline and all subsequent visits. More frequent pregnancy tests will be performed throughout the study if required per local/country requirements. If urine pregnancy test (which is performed at the site) is negative, begin or continue dosing. If urine pregnancy test is positive, withhold dosing and perform a serum pregnancy test. Pregnant subjects must discontinue from study drug treatment. Refer to Section 5.3.1.1 Study Procedures Pregnancy Test for additional details.

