4.3 Sample Size

The planned total sample size of approximately 1640 for this study (with 2:2:2:1:1 randomization ratio for upadacitinib 15 mg, upadacitinib 30 mg, adalimumab 40 mg eow and placebo subjects) provides at least 90% power for a 20% difference in ACR20 response rate (assuming a placebo ACR20 response rate of 30%). It will also

provide at least 90% power for the majority of the key secondary endpoints. With the given sample size, there is approximately 90% power to detect a standardized effect size of 0.26 in change from baseline in SHS for each upadacitinib dose group versus the combined placebo group at Week 24. This sample size will also provide at least 85% power for evaluating non-inferiority for each upadacitinib dose group vs. adalimumab in ACR20 response rate at Week 12 assuming 50% ACR20 response rates for adalimumab and upadacitinib and 30% ACR20 response rates for placebo. All power and sample size calculations are performed at a two-sided significance level of 0.025 and accounting for a 10% dropout rate.

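### If the SHS random-coefficient sensitivity model fails to converge, the fallbacks named in SAP 9.2.3 discard the baseline-to-later covariance and overstate the standard error of the progression-rate difference

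*SAP*

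**What the plan says.** Under Radiographic Endpoints, SAP 9.2.3 tests change from baseline in SHS at Week 24 (ranked endpoint 4) by ANCOVA with linear extrapolation. Multiple imputation and an as-observed ANCOVA serve as further checks.

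A separate sensitivity analysis is a random-coefficient model in which "SHS measurements are used as the response variable, including measurements at Baseline and post-Baseline". Each subject gets a random intercept and a random time slope, and the covariance structure may differ by treatment group. The reported quantity is the treatment-by-time coefficient, read as the difference in progression per 24 weeks.

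Should the fit fail for lack of convergence, the SAP provides that "a simplified model may be explored by removing the random intercept or fitting a fixed-effect linear effect model". For that case it names no repeated-measures covariance, robust standard error or baseline adjustment.

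Hand and foot films are scheduled for everyone at Screening and Week 24. Protocol Appendix C, footnote m, adds a Week 16 film for subjects who meet the rescue criteria and says "An x-ray examination at Week 16 is not required for subjects with at least a 20% improvement" in joint counts.

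**The concern.** The slope difference is a within-subject contrast: it compares each subject's later film with that subject's own baseline film. SHS is a cumulative damage score running from 0 to 528 (SAP 9.4.25, Table 10), so subjects can differ widely in level while changing little over 24 weeks. In this model the random intercept carries that between-subject spread. Without it, the spread in level goes into the standard error of the slope.

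At stake is how one robustness check would be read. Prevention of structural progression is a stated secondary objective. A wide interval from the simplified model could be taken as a lack of robustness when it comes only from the choice of covariance.

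**Working it through.** **Inputs.** 410 subjects per upadacitinib arm and 205 + 205 = 410 on combined placebo (Protocol 5.1). SAP 4.3 claims "approximately 90% power to detect a standardized effect size of 0.26 in change from baseline in SHS" and adds: "All power and sample size calculations are performed at a two-sided significance level of 0.025 and accounting for a 10% dropout rate". Hence 410 x 0.9 = 369 per arm. The documents give no SD or within-subject correlation for SHS, so r is assumed and varied.

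**Step 1: reproduce the planned power.** In units of the SD of the 24-week change, the standard error of the difference is sqrt(2/369) = 0.0736. The noncentrality is 0.26/0.0736 = 3.53. With z = 2.241 for two-sided 0.025, power is Phi(3.53 - 2.24) = 90.15%, which agrees with the stated figure.

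**Step 2: what the fallback does to the covariance.** Put baseline at time 0 and Week 24 at time 1, with variance V at both.

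- Full model: the covariance of the two films is the intercept variance, plus any intercept-slope covariance.
- Slope only: the random slope contributes nothing at time 0, so the covariance between baseline and any later film is zero.
- No random effects: all covariances are zero.

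The slope variance per arm should be 2V(1 - r)/n. Under either fallback the model computes 2V/n. The ratio of standard errors is therefore k = 1/sqrt(1 - r), which equals sqrt(2) x SD(SHS)/SD(24-week change).

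**Step 3: effect on rejection.** With complete pairs, the point estimate and its true sampling SD do not change; only the reported standard error does. The chance of rejecting is about Phi(3.53 - k x z). The SAP assigns no alpha to this sensitivity model, so two levels are shown.

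| Assumed r | k | Reported SE (true 0.0736) | Power, two-sided 0.025 | Power, two-sided 0.05 |
|---|---|---|---|---|
| intercept kept | 1.00 | 0.074 | 90% | 94% |
| 0.5 | 1.41 | 0.104 | 64% | 78% |
| 0.7 | 1.83 | 0.134 | 29% | 48% |
| 0.8 | 2.24 | 0.165 | 7% | 20% |
| 0.9 | 3.16 | 0.233 | 0.02% | 0.4% |
| 0.95 | 4.47 | 0.329 | about 0 | about 0 |

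A threefold inflation needs r = 1 - 1/9 = 0.89, that is, an SD of SHS about 2.1 times the SD of the change (3/sqrt(2) = 2.12).

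**Step 4: checks.** Simulation of complete pairs (4,000 trials per value of r) gave SE ratios of 1.41, 2.24, 3.16 and 4.47 at r = 0.5, 0.8, 0.9 and 0.95. Power without the intercept was 64%, 7%, 0 and 0, against 89% to 91% for the paired analysis. REML fits with some Week 16 films added (four data sets per value) gave slope-only ratios of 1.41, 2.26, 3.15 and 4.57, the same as with no random effects. At r = 0.99 the full-model fits were not reliable (mean SE 0.137 against an expected 0.074), so that value is not used.

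**The case against.** The algebra is hard to dispute; the reach of the point is not. Four inferences that a reader might draw go too far.

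- *The fallback could block ranked endpoints 5 to 14.* It could not. ANCOVA decides endpoint 4, and the random-coefficient model has no role in the alpha transfers described in SAP 9.2.5. The error is also conservative, so it cannot create a false positive.
- *The fallback is what will happen.* The text is conditional and permissive. Most subjects have two films, which give three second moments per arm. A random intercept, a random slope and a residual use three parameters; only an added intercept-slope covariance, which the SAP does not mention, makes four. Week 16 films and varying film dates add information, and a weakly identified model may give a boundary estimate rather than non-convergence. The documents do not show that non-convergence is likely.
- *The standard error is several times too large as a matter of fact.* That depends on r. At r = 0.5 the factor is only 1.4.
- *Robustness of the SHS result rests on this model.* Multiple imputation, as-observed ANCOVA and an optional rank-based ANCOVA stand beside it and are untouched.

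Two further objections stand in part. The term fixed-effect model might have been meant to include a repeated-measures covariance, in which case the loss would not arise for that option, but the SAP does not say so. In the slope-only option, Week 16 and Week 24 films can still correlate; the covariance that matters here, between baseline and later films, is still lost.

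Timing also limits the effect. SAP 11.1 says the primary efficacy analysis was completed under version 3.0 and that version 4.0 governs only later long-term reporting. Appendix F dates the Week 24 lock to January 2020. From Week 104, SAP 9.3 uses MMRM for continuous radiographic endpoints.

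**Conclusion.** The point holds in this limited form: as written, both named simplifications discard the baseline-to-later covariance, and the model would then report a standard error for the slope difference that is too large by 1/sqrt(1 - r). The direction is certain for any positive r, provided no other covariance is added. The size is conditional: a factor of 1.4 to 4.5, and power of 64% down to about zero, for r from 0.5 to 0.95. These figures assume complete pairs and equal variance at both films. A high r is plausible for a cumulative score in subjects whose disease duration spans 5 years or less to more than 10 (the subgroups in SAP Table 7), but this is a judgement and not a figure from the documents.

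The consequence is a possible false failure to confirm in one contingent sensitivity analysis. The primary inference on SHS, type I error control and the other SHS checks are unaffected.

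**What to change.** Replace the fallback sentence in SAP 9.2.3 with an ordered simplification that keeps the within-subject covariance: first drop any intercept-slope covariance, then drop the random slope and keep the random intercept. An equally good alternative is a repeated-measures model with visit as a factor and an unstructured covariance by treatment group. This would match the plan's own practice, since the Week 24 MMRM in SAP 9.1.2 already uses an unstructured matrix. In one simulated fit (200 per arm, r = 0.95) the random-intercept model gave an SE of 0.032, against 0.033 for the full model and 0.147 for slope only.

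The wording change alone cannot alter the completed Week 24 output. The sponsor should therefore also state whether the fallback was used there. If it was, that sensitivity analysis should be rerun with the covariance retained and labelled post hoc. The cost is one sentence and at most one rerun, with no change to data collection or visits.
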